7.1.1. Adverse Events of Special Interest (AESI)

The following TEAEs are considered as the adverse events of special interest (AESI), and will be summarized by AESI Category and PT for each treatment group:

Table 3: Adverse Events of Special Interest (AESI)

| AESI Category | Definition |
|---|---|
| Potential of aminoglycoside renal toxicity | 
 SMQ: Acute renal failure (Narrow and Broad), and; Concomitant medication using the WHODD ATC code J01G |
| Long-term cardiovascular effects including changes in lipid profile | 
 SMQ: Dyslipidaemia (Narrow), or; SOC: Cardiac disorders |
| Hypertension with use of concomitant systemic corticosteroids | 
 SMQ: Hypertension (Narrow and Broad), and; Concomitant medication using the WHODD ATC code H02A |
| Renal toxicity | 
 SMQ: Acute renal failure (Narrow and Broad) |
| Hepatic toxicity | 
 SOC: Hepatobiliary disorders, or; HLGT: Hepatobiliary Investigations |
| Malignancies in general | 
 SOC: Neoplasms benign, malignant and unspecified (incl cysts and polyps) |

Abbreviations: AESI, adverse event of special interest; SMQ, Standardized MedDRA Query; ATC, Anatomical Therapeutic Chemical; SOC, System Organ Class; HLGT, High Level Group Term; WHODD, World Health Organization Drug Dictionary

For potentiation of aminoglycoside renal toxicity and hypertension with use of concomitant systemic corticosteroids, the concomitant medications are those started prior to the onset of corresponding AE.

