7.1.2. Adverse Events of Special Interest

The following AEs are considered as the adverse events of special interest (AESI), and will be summarized by AESI Category and PT:

Table 3: Adverse Events of Special Interest (AESI)

| AESI Category | Definition |
|---|--|
| Potentialization of aminoglycoside renal toxicity | 
• SMQ: Acute renal failure (Narrow and Broad), and;• Concomitant medication using the WHODD ATC code J01G |
| Long-term cardiovascular effects including changes in lipid profile | 
• SMQ: Dyslipidaemia (Narrow), or;• SOC: Cardiac disorders |
| Hypertension with use of concomitant systemic corticosteroids | 
• SMQ: Hypertension (Narrow and Broad), and;• Concomitant medication using the WHODD ATC code H02A |
| Renal toxicity | 
• SMQ: Acute renal failure (Narrow and Broad) |
| Hepatic toxicity | 
• SOC: Hepatobiliary disorders, or;• HLGT: Hepatobiliary Investigations |
| Malignancies in general | 
• SOC: Neoplasms benign, malignant and unspecified (incl cysts and polyps) |

For potentialization of aminoglycoside renal toxicity and hypertension with use of concomitant systemic corticosteroids, the concomitant medications are those started prior to the onset of corresponding AE.
Abbreviation: AESI = adverse event of special interest; SMQ = Standardized MedDRA Query; ATC = Anatomical Therapeutic Chemical; SOC = System Organ Class; HLGT = High Level Group Term; WHODD = World Health Organization Drug Dictionary

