7.1. Adverse Events

AEs will be coded to the MedDRA (Version 24.1 or higher) lower level term closest to the verbatim term. The linked MedDRA PT and primary system organ class (SOC) are also captured in the database. The severity of AEs will be graded using the latest version of the Common Terminology Criteria for Adverse Events (CTCAE), Version 5.0 whenever possible.

For the double-blind treatment period, a treatment-emergent adverse event (TEAE) is defined as an adverse event that:

- Occurs or worsens during the double-blind treatment period (Day 1 to within 4 weeks of last double-blind treatment, and prior to the first open-label treatment) for subjects who complete the double-blind treatment period; and
- Occurs or worsens from the period extending from Day 1 to 4 weeks after the last dose of double-blind study drug for subjects who discontinue from the study early during the double-blind treatment period, or who complete double-blind treatment period but not enroll into open-label treatment period.

Only those AEs that are treatment-emergent will be included in summary tables. All AEs, treatment-emergent or otherwise, will be presented in subject data listings. An overview table of TEAEs, including number of subjects with TEAEs, treatment-emergent serious adverse events (TESAEs), deaths, TEAEs classified as CTCAE Grade 3 or higher, study drug related TEAEs, TEAEs leading to study drug withdrawal will be provided for each treatment group. The following summaries will be produced for the TEAEs by treatment group:

- Incidence of TEAEs by SOC and PT
- Incidence of TEAEs by PT in descending order
- Incidence of treatment-related TEAEs by SOC and PT
- Incidence of TEAEs by SOC, PT, and maximum CTCAE grade
- Incidence of TEAEs by SOC, PT, and relationship to treatment.

In the summary tables subjects may be counted under multiple SOC and PTs, but for each SOC and PT, subjects are only counted once. If a subject has the same AE on multiple occasions, the highest severity (5=fatal, 4=life-threatening, 3=severe, 2=moderate, 1=mild) recorded for the event will be presented and the highest drug relationship (1 = 'Unrelated', 2 = 'Unlikely to be Related', 3 = 'Possibly Related', 4 = 'Probably Related'), reclassified into Related ('Possibly Related', 'Probably Related') or Not Related ('Unrelated', 'Unlikely to be Related'), will be presented on the respective tables.

The following summaries will also be presented for the TESAEs:

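### In Table 3 of both SAPs the malignancy AESI category is defined by the whole neoplasm SOC, so its total by arm counts any neoplasm, not malignancies

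*SAP*

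**What the plan says.** Both SAPs define six AESI categories in a Table 3. In the double-blind SAP (7.1.1) the last is "Malignancies in general", and its definition is a single line: "SOC: Neoplasms benign, malignant and unspecified (incl cysts and polyps". The open-label SAP (7.1.2) gives the same label and the same single line.

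The double-blind SAP applies the table to treatment-emergent events ("The following TEAEs are considered as the adverse events of special interest (AESI") and says they "will be summarized by AESI Category and PT for each treatment group". The open-label SAP says its AESIs "will be summarized by AESI Category and PT", and its Section 7 presents safety by treatment group and overall.

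On coding, the double-blind SAP (7.1) states: "The linked MedDRA PT and primary system organ class (SOC) are also captured in the database". The open-label SAP (7.1) says the same.

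**The concern.** The label names one harm and the rule selects a wider set of events. By its own title the system organ class covers benign and unspecified neoplasms, cysts and polyps. If the rule is programmed as written, the category line for each arm is the number of boys with any neoplasm, shown under a heading that says malignancies.

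Malignancy is one of only six topics the sponsor singled out for special attention. A category total is the number most likely to be lifted from the table into a report text or a safety summary, where the preferred-term rows beneath it may not follow.

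**Working it through.** No figure in the plan is tied to this category, so there is nothing to reproduce. The check is a comparison of label and rule, a search for a restriction, and a look at what the total measures.

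**1. Label against rule, all six rows (Table 3, both SAPs).**

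| Category (paraphrased) | Rule | Does the rule's own name go beyond the label? |
|---|---|---|
| Aminoglycoside-related renal toxicity | Acute renal failure SMQ, narrow and broad, and ATC J01G | No |
| Cardiovascular and lipid effects | Narrow dyslipidaemia SMQ, or the whole cardiac SOC | No |
| Hypertension with systemic corticosteroids | Hypertension SMQ, narrow and broad, and ATC H02A | No |
| Renal toxicity | Acute renal failure SMQ, narrow and broad | No |
| Hepatic toxicity | Whole hepatobiliary SOC, or a hepatobiliary HLGT | No |
| Malignancies | Whole neoplasm SOC | Yes: it names benign lesions, cysts and polyps |

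A whole SOC is used in three of the six rows, so breadth is not peculiar to this one. What sets it apart is that the SOC's own title contradicts the label.

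**2. Is there a restriction elsewhere?** The malignancy row has no added condition. The note to Table 3 on concomitant-medication timing concerns the aminoglycoside and hypertension rows only. Protocol 9.4.7 lists events for special attention but has no malignancy definition. The separate document on changes from the planned analysis deals with efficacy, and the open-label SAP's version history lists no change to the AESIs. No preferred-term list, query or medical review narrows the row.

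**3. What the total measures.** For one arm, let

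- T = boys with at least one event in the SOC (the category total)
- M = boys with at least one malignant or unspecified event
- B = boys whose only events in the SOC are benign

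Then T = M + B, and the over-count is T − M = B. If B = 0 the total is right despite the label. The documents give neither B nor M, nor any rate from which to derive them, so the size stays unknown.

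**4. What can still be recovered.** The tabulation is also by preferred term, so the terms that make up T are visible. The SOC-and-PT tables in 7.1 of each SAP already report the same SOC total under its proper name.

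**5. The open-label table.** Early-start boys can have ataluren from randomization to Week 144 (144 weeks), and delayed-start boys from Week 72 to Week 144 (144 − 72 = 72 weeks). Assume full follow-up, equal arm sizes, and the same low constant rate of benign events per week in both groups. The expected ratio of crude benign counts is then 144 / 72 = 2. The open-label SAP (7.1.1) specifies exposure-adjusted rates by SOC and PT, but 7.1.2 does not specify them by AESI category. Exposure alone would therefore tend to give a higher total in the early-start group, under a heading that reads as cancer. The factor of 2 is a ratio under those assumptions and says nothing about how many events there are.

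**The case against.** The strongest reply is that the same sentence that creates the category also requires the preferred-term breakdown. A true malignancy would stand in its own row, serious events and deaths are listed separately, and events are also tabulated by SOC, PT and maximum grade. A SOC-wide search is sensitive and does not depend on a hand-made list. The table is descriptive: no test, threshold or stopping rule is attached. All of this stands, and it limits the point to the category line.

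A reader might infer four stronger things that the documents do not support:

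- *That a real malignancy would be hidden or diluted.* It would not, because the preferred term is shown.
- *That cancers are missed.* Any malignant event coded to this SOC is captured.
- *That this row alone is broad.* The cardiovascular and hepatic rows each include a whole SOC, and three other rows use broad SMQs. The table does also use narrower tools, such as "SMQ: Dyslipidaemia (Narrow), or", but broad capture is common in it.
- *That a false cancer signal between arms is likely.* That needs a benign-event rate, and none is given. Any illustrative split of counts would rest on an invented rate.

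It can also be said that the exposure-adjusted SOC line in the open-label SAP gives a fair comparison of the same events. That is correct, but it does not mend the AESI line, which carries a different name and no adjustment.

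**Conclusion.** The point holds as a minor one. In both SAPs the category total titled malignancies is a count of any neoplasm. The error lies in the specificity and label of that one line. The preferred-term rows, the capture of malignant cases coded to the SOC, the efficacy analyses, the error rate and the sample size are unaffected.

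The size of the over-count cannot be stated and may be nil. The conclusion assumes that the category is programmed as written, from the SOC held in the database, with no restriction recorded outside the supplied documents. The remark on the open-label table also rests on the equal-rate, equal-arm-size and full-follow-up assumptions given in the working.

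**What to change.** In Table 3 of both SAPs, keep the SOC search but name the row for what it contains, for example *Neoplasms, any (benign, malignant, unspecified)*.

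- **Open-label SAP:** add a sub-row for malignant or unspecified terms, defined by a documented query or preferred-term list, and fix it before the final lock, which the SAP describes as still to come.
- **Double-blind data:** the soft lock was on 11 April 2022 and results by arm have been produced, so a new list can no longer be presented as fixed before unblinding. Relabel the row and flag the malignant preferred terms within it. Neither step changes which events are counted.

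The cost is about one table line per SAP, a short term list and a small programming change. No data are added or lost, and the broad view remains in the row itself and in the SOC-and-PT tables.

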3.2 Inclusion Criteria

Subjects must meet all of the following conditions to be eligible for enrollment into the study:

1. Evidence of signed and dated informed consent/assent document(s) indicating that the subject (and/or his parent/legal guardian) has been informed of all pertinent aspects of the trial. ***Note: If the study candidate is considered a child under local regulation, a parent or legal guardian must provide written consent prior to initiation of study screening procedures and the study candidate may be required to provide written assent. The rules of the responsible institutional review board/ethics committee (IRB/EC) regarding whether one or both parents must provide consent and the appropriate ages for obtaining consent and assent from the subject should be followed.***
2. Male sex.
3. Age ≥ 5 years. When Version 3 is implemented or approximately 270 subjects have enrolled in the study, only subjects aged ≥ 7 to ≤ 16 who meet the mITT criteria will be eligible to enroll.
4. Phenotypic evidence of DMD based on the onset of characteristic clinical symptoms or signs (eg, proximal muscle weakness, waddling gait, and Gowers' maneuver) by 6 years of age and an elevated serum creatine kinase (CK). ***Medical documentation of phenotypic evidence of DMD needs to be provided upon request by the PTC Therapeutics medical monitor.***
5. Documentation of the presence of a nonsense point mutation in the dystrophin gene as determined by gene sequencing. ***Note: Review and approval of documentation by sponsor or designee is required prior to enrollment.***

6. Use of systemic corticosteroids (prednisone/prednisolone or deflazacort) for a minimum of 12 months immediately prior to start of study treatment, with no significant change in dosage or dosing regimen for a minimum of 3 months immediately prior to start of study treatment and a reasonable expectation that dosage and dosing regimen will not change significantly for the duration of the study. **Note: Daily, every other day, high-dose weekend, and intermittent regimens permitted only. The doses recommended or required are shown in Table 1. Increases in corticosteroid dose to adjust for increases in body weight will not exclude a subject from participation.**

Table 1. Corticosteroid Regimens and Doses Recommended or Required

Regimen	Prednisone/Prednisolone	Deflazacort
Daily	0.75 mg/kg (recommended) At least 0.3 mg/kg (required)	0.9 mg/kg (recommended) At least 0.3 mg/kg (required)

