5.4.2 Aminoglycosides and Vancomycin

Ataluren should not be co-administered with IV aminoglycosides (eg, tobramycin, gentamicin, amikacin, kanamycin and/or IV vancomycin), based on cases of decreased renal function observed in a clinical trial of ataluren in patients with nmCF. Elevations of serum creatinine occurred in several nmCF patients treated with ataluren and IV aminoglycosides/vancomycin together with other antibiotics for cystic fibrosis exacerbations. The serum creatinine elevations resolved in all cases, with discontinuation of the IV aminoglycoside/vancomycin, and either continuation or interruption of ataluren. These findings suggested that co-administration of ataluren and IV aminoglycosides/vancomycin may potentiate the nephrotoxic effect of these antibiotics. For additional details, refer to the Investigator Brochure.

In subjects who require treatment for serious infections, investigators should substitute other antibiotics for systemic aminoglycosides/vancomycin when clinically appropriate. For subjects requiring systemic antibiotic therapy, IV aminoglycosides/vancomycin may be used when medically necessary. However, consideration should be given to use of alternative agents if appropriate. If IV aminoglycosides/vancomycin are administered, study drug must be interrupted during the course of these antibiotic treatments. Subjects requiring IV aminoglycoside or IV vancomycin therapy should be closely monitored in an appropriate setting, such as a hospital. In subjects receiving potentially nephrotoxic agents such as IV aminoglycosides or IV vancomycin, antibiotic drug levels (if appropriate) and serum creatinine and blood urea nitrogen (BUN) should be followed closely. The antibiotic trough level (if appropriate) and creatinine and BUN should be measured within 24 to 48 hours of administration of the first antibiotic dose, and further antibiotic dosing should be based on these results. Creatinine and BUN should be measured prior to initiating IV aminoglycoside or vancomycin therapy and at least weekly during the course of antibiotic treatment.

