5.7. Concomitant Medications and Non-Drug Treatments for the On-Ataluren Treatment Period

Concomitant medications and non-drug treatments will be coded using the World Health Organization Drug Dictionary (WHODD), version September 2021 or higher.

Concomitant medications and non-drug treatments during the on-ataluren treatment period are defined as those taken any time from the first dose date of Ataluren through the last follow up date within study.

The use of concomitant medications and non-drug treatments will be summarized by Anatomical Therapeutic Chemical Level 3 and preferred term (PT) based on ITT, and as-treated-OL population. In addition, the use of corticosteroids and the changes in regimen of corticosteroids will be also summarized during overall treatment period for ITT population, and during on-ataluren treatment period for as-treated-OL population.

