5.7. Concomitant Medications and Non-Drug Treatments

Concomitant medications and non-drug treatments will be coded using the World Health Organization Drug Dictionary (WHODD), version September 2021 or higher.

Prior medications and non-drug treatments are defined as those taken any time prior to Day 1. Concomitant medications and non-drug treatments for double-blind period are defined as those taken any time during the double-blind treatment period (Day 1 to the date prior to the first dose of open-label study treatment, inclusive).

The use of prior and concomitant medications and non-drug treatments will be summarized by Anatomical Therapeutic Chemical (ATC) Level 3 and preferred term (PT) for ITT, mITT, and as-treated populations. In addition, corticosteroids use at baseline and the incidence of changes in regimen of corticosteroids will be summarized for ITT, mITT, and as-treated populations.

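### The aminoglycoside renal AESI counts renal events long after a finished course and has no vancomycin criterion, so it can misclassify events and covers only part of the stated risk

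*SAP*

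**What the plan says.** Table 3 of the double-blind SAP (Section 7.1.1) and Table 3 of the open-label SAP (Section 7.1.2) contain the same three relevant rows.

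- **Aminoglycoside renal toxicity:** an event in "SMQ: Acute renal failure (Narrow and Broad") together with "Concomitant medication using the WHODD ATC code J01G".
- **Renal toxicity:** the same SMQ with no co-medication condition.
- **Hypertension with systemic corticosteroids:** a Hypertension SMQ event together with "Concomitant medication using the WHODD ATC code H02A".

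For the two rows with a drug condition, both SAPs add one timing rule: "the concomitant medications are those started prior to the onset of corresponding AE".

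Section 5.7 of each SAP defines concomitant use. In the double-blind SAP it means "those taken any time during the double-blind treatment period (Day 1 to the date prior to the first dose of open-label study treatment, inclusive"). In the open-label SAP it means "those taken any time from the first dose date of Ataluren through the last follow up date" within the study.

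Protocol 5.4.2 describes the risk behind the renal row: "co-administration of ataluren and IV aminoglycosides/vancomycin may potentiate the nephrotoxic effect of these antibiotics". Exclusion criterion 2 covers both antibiotics, and 5.4.2 requires study drug to be interrupted while either is given. Neither SAP mentions vancomycin.

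**The concern.** A row meant to show possible potentiation of antibiotic nephrotoxicity should pick out renal events that occur while the antibiotic could plausibly be acting. Here, once a qualifying drug has started, every later event in the SMQ is included, however long ago the course ended. Events on the other antibiotic that the protocol names are not included unless the subject also started an aminoglycoside earlier.

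This interaction is the reason for an exclusion criterion and for a mandatory interruption of study drug. A reader will go to this row to judge it. As defined, the row mixes plausible and implausible events and leaves out half of the named drug pair. If antibiotic courses are few (an assumption, since the documents give no count), one misplaced event could change how the row reads.

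**Working it through.** There is no figure in the plan to reproduce. The check sets the definitions side by side and works out how far the timing rule reaches.

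**Step 1. Does the definition of concomitant use repair the timing rule?** Only in part. A course that ended before Day 1 (double-blind) or before the first ataluren dose (open-label) does not count. A course taken at any time in the period does count, and nothing requires it to be ongoing or recent at onset.

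**Step 2. How long a gap does the rule allow?** The inputs are the 72-week and 144-week treatment durations and the 4-week treatment-emergent tail after the last dose (Section 7.1 of each SAP).

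- Double-blind, subject entering open label: up to about 72 weeks.
- Double-blind, subject completing but not entering open label: 72 + 4 = 76 weeks.
- Open-label SAP, early-start: 144 + 4 = 148 weeks.
- Open-label SAP, delayed-start: about 72 + 4 = 76 weeks on ataluren.

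**Step 3. Illustration.** Take a hypothetical aminoglycoside course from Week 4 to Week 6.

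- Double-blind: an event qualifies during 72 − 4 = 68 weeks. Of these, 72 − 6 = 66 fall after the course ended, and 66/68 = 97%.
- Early-start over 144 weeks: 144 − 4 = 140 qualifying weeks, of which 144 − 6 = 138 are after the course, and 138/140 = 99%.

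These are shares of calendar time for one invented course. They are not misclassification rates.

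**Step 4. How are typical events classified?** This assumes that J01G does not include vancomycin.

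| Renal SMQ event | Interaction row now | Renal toxicity row | With overlap, look-back and vancomycin |
|---|---|---|---|
| During an aminoglycoside course | Counted | Counted | Counted |
| Soon after the course | Counted | Counted | Counted if inside the window |
| Many weeks after the course | Counted | Counted | Not counted |
| During vancomycin, no aminoglycoside taken | Not counted | Counted | Counted |
| During vancomycin, aminoglycoside started earlier | Counted, on the aminoglycoside | Counted | Counted, on the vancomycin |
| After a course that ended before Day 1 | Not counted | Counted | Not counted |

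The third and fourth lines are the problem. The first shows that the present rule loses no on-course aminoglycoside event.

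**Step 5. Hypertension row.** Criterion 6 requires "Use of systemic corticosteroids (prednisone/prednisolone or deflazacort) for a minimum of 12 months immediately prior to start of study treatment", and Protocol 5.4.1 asks for a stable regimen through the 72 double-blind weeks. The H02A condition is therefore met by essentially every subject, including one who later stops steroids. The row is close to a count of all Hypertension SMQ events, and an overlap rule would change it little.

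**The case against.** The strongest reply is that a wide net is reasonable for safety screening. A start-before-onset rule keeps every event that begins during or after a course, whereas a strict overlap rule could drop renal events that begin just after one. Vancomycin events still appear under Renal toxicity. Both SAPs also summarise renal laboratory threshold values regardless of co-medication and provide by-subject listings in date order, so a handful of cases could be reviewed individually. The row is named for aminoglycosides, and the renal cases cited in the protocol came from cystic fibrosis patients, so exposure here may be rare.

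Much of this stands. It limits the point to classification and coverage, and it is why the fix needs a look-back and not bare overlap. It does not justify the rule as written, because the unconditional Renal toxicity row already provides the wide net. The interaction row adds information only if it is more specific.

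A reader might infer more than the documents support:

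- **That the table cannot show the aminoglycoside interaction.** It can, because on-course events are retained, though mixed with later ones.
- **That vancomycin events are lost.** They are counted, but not identifiable as possible interactions.
- **That the safety conclusion on co-medication is wrong.** No conclusion in the documents is said to rest on this row alone.
- **That the hypertension row is invalid.** In the double-blind period it still supports a randomised comparison on background steroids.

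**Conclusion.** The point holds as a classification and coverage defect in both SAPs. The renal interaction row can include events unrelated in time to the antibiotic, with a possible gap of up to about 76 weeks in the double-blind period and about 148 weeks for early-start subjects overall. It addresses only the aminoglycoside part of the risk in Protocol 5.4.2. It drops no on-course aminoglycoside events, and general renal surveillance is unaffected. The numerical effect cannot be sized because the documents report neither antibiotic exposure nor renal event counts.

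The vancomycin part rests on an assumption: that J01G does not include vancomycin. The documents show only a single code in a row labelled for aminoglycosides, and they do not give the code's contents. If the code did include vancomycin, that gap would shrink to one of labelling, and the timing defect would remain.

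The protocol's interruption requirement adds a further limit. A subject managed as planned is off study drug during the course, so an event there is hard to interpret without study-drug status at onset, which the row does not report.

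The hypertension row is a minor labelling matter.

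**What to change.** These changes concern analysis only and alter no clinical rule.

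1. **Exposure rule.** Replace the timing footnote for the renal interaction row with: drug start ≤ AE onset ≤ drug stop + a fixed look-back window. The sponsor should choose the window and state its reason.
2. **Vancomycin.** Add an IV vancomycin criterion to the interaction category.
3. **Context.** Report study-drug status at onset (on or interrupted) and the number of subjects exposed to each antibiotic per arm, as the denominator.
4. **Broad screen.** Keep the unconditional Renal toxicity row unchanged.
5. **Hypertension row.** Label it as all Hypertension SMQ events and show corticosteroid status at onset.

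Make the change in the open-label SAP before the final database lock, which that document describes as still to come. The double-blind data were soft-locked on 11 April 2022 and results have since been reported, so there the revised row can only be a supplementary table labelled as added after lock. Data up to Week 72 also feed the open-label analysis, so the window should be justified on grounds independent of those results.

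The cost is a footnote, one added drug criterion and a modest programming change, plus date imputation for partial stop dates. This assumes that stop dates are collected. The protocol says that concomitant medication information is recorded but does not list the date fields, so this should be confirmed first.
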